3.2 Exclusion Criteria

A patient who has any of the following criteria will be excluded from the study:

1. Diagnostic MMG shows prominent calcification in the index lesion.
2. Triple negative cancers (ER-ve and PR-ve and HER2-ve) where ER and PR positivity is defined as $\geq 1\%$ staining on IHC(57)
3. Previous in-situ or invasive breast cancer
4. Patients who have had a mastectomy
5. Extensive DCIS (Extensive Intraductal Component (EIC)). Extensive DCIS is defined as invasive carcinoma with the following three components:
 - a. DCIS is present within the invasive tumour; and
 - b. DCIS within invasive tumour comprises more than 25% of the invasive tumour volume; and
 - c. DCIS exists beyond the margin of the invasive tumour
6. Lymphovascular invasion; Multifocal/multicentric breast cancer; Distant metastasis at diagnosis or bilateral breast cancer
7. HER2 positive patients who will not receive trastuzumab as part of adjuvant systemic therapy
8. Gene carriers (BRCA 1,2) or those whose family history of breast cancer reaches the high-risk category of the Cancer Australia (refer to Appendix E)

9. Contraindication to MRI scanning (estimated glomerular filtration rate (eGFR) <30 ml/min/1.73m², pacemaker, implanted non MRI compatible devices, cochlear implants, neurostimulators, insulin infusion pumps, pregnancy or lactation)
10. Moderate or marked background parenchymal enhancement on pre-operative MRI. In the event of an interpretation discrepancy between the local site and the central review, the central review interpretation will be used to determine eligibility.
11. Concurrent illness/conditions which limits life expectancy to 5 years.

3.3 Substudies of Pre-registered Patients (Appendices I & J)

Patients who have had MRI and subsequently been deemed ineligible for the main study will be asked to consent for further research on descriptive analyses.

4 RECRUITMENT

A secure web-based screening log has been developed to keep a record of screened potential participants. The screening log will be made available to study nurses/data managers at participating institutions; these staff can only access the screening log specific to their own institution.

The BCT website (www.breastcancertrials.org.au) public access area contains a section dedicated to the ANZ 1002: PROSPECT trial where women can obtain information about the trial.

BCT will actively promote the trial throughout Australia and New Zealand through newsletters and cancer consumer networks (e.g. the Breast Cancer Network Australia). BCT may promote this trial to the general public by generating media releases, community service announcements, advertising and producing YouTube videos. Staff at participating institutions will also be encouraged to promote the trial locally.

5 REGISTRATION PROCEDURES

BCT institutions will pre-register and register patients via the BCT website (www.breastcancertrials.org.au).

Patients will be recruited from investigators' clinical practices. Patients will sign a 'consent to screen' form at the pre-registration step. A separate written informed consent must also be signed by the patient and investigator prior to registration.

5.1 Pre-registration

1. Obtain written informed consent for pre-operative MRI scan, signed and dated by the patient and investigator.
2. Access the PROSPECT online registration system (www.breastcancertrials.org.au) and perform pre-registration. The data listed below will be collected:
 - Date of birth
 - Physical examination
 - Menopausal status (refer to appendix G)
 - Concurrent serious illnesses
 - Family history
 - Primary tumour receptor status (ER, PR and HER2 neu by IHC)
 - Biochemistry (eGFR)
 - Diagnostic imaging (mammogram and ultrasound)

An email confirming that the pre-registration step has been successful and a patient pre-registration code number will be assigned.

3. Conduct the trial specific MRI and surgery. The MRI report and surgical report must be faxed to BCT ([contact]) and data entered in the online registration system.
4. Where requested, allow central radiology reviewers access to imaging (U/S, mammogram, and MRI) which confirms unifocal breast cancer, and, any additional suspicious lesions have been appropriately identified for further assessment (see figure 2).

5.2 Registration

1. Obtain written informed consent for participation in ANZ1002 PROSPECT, signed and dated by the patient and investigator.
2. Consent for tissue banking of the primary tumour will be sought to allow subsequent research studies.
3. Patients must be registered within 8 weeks after final excisional surgery.

4. Verify eligibility (refer to section 3) and confirm receipt of an 'eligible patient' notification email. Where central radiological review is being undertaken, the notification email will not be generated until the review is complete.
5. Access the ANZ1002 PROSPECT online registration system (www.breastcancertrials.org.au), identify the correct patient based on the pre-registration code number and perform registration.

5.3 Post registration

A patient registration number (Patient ID) will be supplied to acknowledge successful registration to the trial. Staff at the institution must enter the Patient ID on the baseline CRFs, submit these to BCT within 2 weeks of registration, and file the original forms in the patient CRF folder.

A forms due schedule will be provided by BCT. This schedule must be followed and CRFs must be submitted within two weeks of each study visit. The Study Calendar (refer to section 6.2) and forms due schedules must be filed in each patient's trial folder, as an aid to the correct timing of protocol assessments.

6 STUDY PROCEDURES

6.1 Required Evaluations

6.1.1 Pre-Surgery/Pre-registration

Patients willing to consider participation in the ANZ1002 PROSPECT study must have unifocal disease on mammography (refer to section 3) have histologically confirmed** ER+ and/or PR+ and/or HER2+ breast cancer, and have signed the screening consent to undergo a pre-operative MRI scan prior to being pre-registered.

** Oestrogen receptor and progesterone receptor status of invasive cancer will be assessed by immunohistochemistry on the diagnostic specimen. The IHC results will be reported as percentage of nuclei stained and a score of intensity from negative, weak, intermediate or high staining

- HER2 neu status will be assessed by immunohistochemistry and will be scored as follows⁽⁵⁹⁾:
 - 0 or 1+ (HER2 negative) No staining (0) or <10% of cancer cells show weak to moderate staining (1+)
 - 2+ (equivocal) <10% of cancer cells show strong complete membrane staining (rare) or 10–30% of cancer cells show weak to moderate complete membrane staining or strong cytoplasmic staining is present, making assessment of membrane staining difficult
 - 3+ (HER2 positive) >30% of cancer cells show strong, complete membrane staining without cytoplasmic staining and without staining of normal breast tissue (ASCO/CAP: 30% rather than 10%).

6.1.1.1 MRI protocol

Each site will nominate one MRI facility to undertake all study MRIs. All sites must agree to the study requirements for MRI protocols as outlined in this section.

MRI is not suitable for patients with any of the following (refer to section 3.2): pacemaker, implanted non-MRI compatible devices, cochlear implants, neurostimulators, insulin infusion pumps, (eGFR) <30 ml/min/1.73m².

Compatibility checks are required for: aneurysm clips, those with a history of metallic ocular foreign bodies, vascular coils, stents and filters, eye implants and heart valve replacements.

- If there is more than mild background parenchymal enhancement, the patient is not eligible for the study and will be managed according to the usual guidelines.
- If there are any suspicious lesions other than the known cancer, these are biopsied prior to or at surgery and managed appropriately (see section 6.1.3).
- If the additional lesions are not DCIS or invasive cancer, the patient is still potentially eligible for the trial.

Uniform scanning parameters will require women to be prone, with breasts placed in the MRI coils and minimal lateral compression to maintain immobilisation. The following settings will be used:

1. Pre-contrast

Bilateral axial scans including T1 (3D acquisition) and T2 sequences one of which is not fat saturated. Isotropic voxel equal to or less than $1 \times 1 \times 1 \text{mm}^3$ for 3d sequences.

2. Dynamic contrast enhanced

Contrast: 0.1mmol/kg body weight of a macrocyclic contrast agent administered intravenously preferably by injector. The dynamic sequence should be fat suppressed and preferably a 3D acquisition with isotropic voxel equal to or less than $1 \times 1 \times 1 \text{mm}^3$. Image acquisition should include a pre-contrast T1 weighted sequence, followed by at least 4 post contrast T1 weighted sequences. The first post-contrast sequence should be timed to coincide with the peak of contrast enhancement, usually in the first 90 seconds, the remaining sequences to follow every 90 seconds.

3. Images are to be presented in unsubtracted and temporal subtracted formats.

4. Enhancement kinetics reviewed on the scanner work-station or CAD work-station

5. BI-RADS⁽⁵⁸⁾ reporting system and double reporting by two experienced breast MR radiologists (at least one of whom is a chief investigator or associate investigator of the study). BI-RADS 3 lesions would ordinarily have a recommendation for 6 month follow up MRI scan. These lesions will be grouped with the BI-RADS 4 lesions and a tissue diagnosis is required.

[figure not shown]
Background parenchymal enhancement will be assessed using the first post contrast series with subtracted and unsubtracted images. **Patients with moderate or marked parenchymal enhancement will be excluded.**

In those patients with no/minimal/mild background parenchymal enhancement, an additional BI-RADS 3-5 mass will require further investigation with US-guided MRI-directed core biopsy or excisional biopsy at primary surgery. Patients who have biopsy-proven additional malignant disease will be excluded.

In those patients with no/minimal/mild background parenchymal enhancement and additional BI-RADS 3-5 non-mass enhancement, a MRI guided biopsy or excisional biopsy at primary surgery will be performed and biopsy-proven additional malignant disease will be excluded.

In those patients with no/minimal/mild background parenchymal enhancement and additional BI-RADS 3-5 foci or focus, a MRI guided biopsy or excisional biopsy at primary surgery will be performed and biopsy-proven additional malignant disease will be excluded.

Figure 2 MRI Protocol

6.1.2 Central imaging review

[figure not shown]
Each pre-registered patient will have the imaging undertaken for screening and staging (U/S, mammogram and MRI) centrally reviewed to confirm eligibility. Central radiology review will be undertaken by radiologists from Royal Melbourne Hospital. Findings and interpretations will be discussed between the site and central radiologists, however eligibility based on imaging will be determined by the central radiologists undertaking the review.

6.1.3 Surgery

6.1.3.1 Surgical Procedures

Patients will undergo wide local excision of the breast cancer and sentinel node biopsy or axillary dissection (in the case of failed or refused sentinel node biopsy). Where an additional mass has been identified by MRI, but not investigated by core biopsy, excisional biopsy at the time of primary surgery is required. The breast specimen shall be orientated in the operating room according to standard hospital protocols. Any intraoperative margin re-excision specimens shall be orientated to allow calculation of the true margin. The true margin is calculated by adding the initial margin to the width of re-excised tissue in the plane of the margin. If the invasive tumour (or DCIS) is within 2 mm of an inked radial margin and has not been re-excised intra-operatively, then this margin must be re-excised to achieve the required margin for the patient to be eligible for the trial. Superficial and deep margins of <2 mm for invasive cancer or DCIS are allowed if these margins are not involved and all breast tissue from the subcutaneous tissue or pectoralis fascia respectively are surgically removed and this is documented in the operative record.

Figure 3 Surgical Management

6.1.3.2 Pathological assessment

Each participating centre should identify a pathologist responsible for handling and reporting information derived from specimens of breast cancer.

Surgical specimens will be assessed according to guidelines from the National Breast and Ovarian Cancer Centre (The pathology reporting of breast cancer. A guide for pathologists, surgeons, radiologists and oncologists (3rd edition 2008)).

For patients pre-registered to ANZ1002 PROSPECT trial the following data must be documented in histopathology reports of breast surgical procedures, specifically:

- Invasive tumour size will be confirmed microscopically
- Resection margin distance ≤ 10 mm will be confirmed microscopically. Distance >10 mm will be recorded as >10 mm
- Lymphovascular invasion will be assessed histologically Immunohistochemistry with CD34 to highlight endothelial cells will be used insuspicious areas
- If not previously done on the diagnostic core, HER2 neu status must be assessed by ISH testing (using HER2 SISH or CISH). Fluorescence in Situ Hybridisation (FISH) will be used in equivocal cases
- Sentinel node biopsy specimens will have sentinel node(s) dissected from adipose tissue. Nodes will be sliced at 2mm interval and placed in a single cassette per node. 3 HE levels at 200 microns will be examined and 1 immunostain with Cam5.2 will be performed.
- Sentinel Nodes will be classified as
 1. negative
 2. isolated tumour cells (tumour cell focus <0.2 mm)
 3. micrometastasis (0.2-2 mm focus)
 4. metastatic focus >2 mm

- Axillary dissection specimens will have individual nodes dissected from adipose tissue and examined by H&E staining
- Ductal Carcinoma in Situ (DCIS)
 - DCIS will be assessed by histology
 - Immunostains with P63 and myosin heavy chain will be used to assist in separating in situ tumour from invasive tumour
 - Extensive DCIS (Extensive Intraductal Component (EIC)). Extensive DCIS is defined as invasive carcinoma with the following three components:
 - DCIS is present within the invasive tumour; and
 - DCIS within invasive tumour comprises more than 25% of the invasive tumour volume; and
 - DCIS exists beyond the margin of the invasive tumour

6.1.4 Post Surgery/Registration

Evaluations must be completed prior to registration unless otherwise specified in the Study Calendar in Section 6.2.

The data listed below will be collected via the Online Registration System:

- Confirmation ECOG performance status is <2
- Histopathology data pertaining to the primary tumour (refer to section 6.1.3.2)

Registered patients will receive systemic therapy as per usual guidelines, but will forego post-operative radiotherapy.

6.1.5 Follow up of patients not eligible for main study participation

See Appendices I and J for data to be collected.

6.1.6 Study visits/Procedures

All patients:

Pre-registration – pre-operative MRI scan (≤6 weeks prior to first excisional surgery).

Post- registration:

- Clinical review every 3 months for the first 6 months post final excisional surgery followed by:
 - 6 monthly review for 5 years
 - 12 monthly review until 10 years or until the final analysis, whichever occurs first
- A mammogram will be performed 6 months post final excisional surgery; annually thereafter
- A MRI will be performed 18 months post final excisional surgery

If a local recurrence is suspected on clinical examination or imaging, the diagnosis will be confirmed with percutaneous biopsy and management will be along usual guidelines, informed by the opinion of the multidisciplinary team at the institution. All suspected ipsilateral invasive recurrences must be reported to BCT on the Suspicion of Ipsilateral Invasive Recurrence (SIIR) form within 24 hours of suspicion. Investigations ordered on the grounds of patient reported findings, clinical palpation, routine imaging or positive cytology constitute suspicion, requiring the submission of the SIIR form. Once histology is available the outcome of the suspicion will be confirmed on the Follow Up (E) form and if necessary Ipsilateral Invasive Recurrence (IIR) forms.

6.1.7 Post-operative radiological surveillance

If the mammogram shows equivocal or suspicious changes, these will be investigated with ultrasound and ultrasound-guided or stereotactic core biopsy as clinically indicated.

If the MRI at 18 months shows any additional mass enhancement or non-mass enhancement or additional foci, these will be investigated with targeted ultrasound and ultrasound or MRI-guided core biopsy to diagnose or exclude local recurrence.

Any local recurrence will be managed with appropriate surgery with or without adjuvant radiotherapy, and the local recurrence must be promptly reported to BCT.

6.2 Study Calendar

	Pre-Registration Visit	Registration Visit	Study Visits				
Month		0	3	6	12	18	24 ⁸
Visit	Screening	0	1	2	3	4	5
Informed Consent ¹ (Screening Consent)	+						
Informed Consent ¹ (Main Consent)		+					
Age, ECOG PS, Medical history, BRCA Status and Cancer Australia risk grouping	+						
Physical Examination ²		+	+	+	+	+	+
Anti-cancer therapy ³		+	+	+	+	+	+
Biochemistry ⁴	+					+	
MRI ⁵	+					+	
Mammogram ⁶	+			+		+	
Adverse Events ⁷	+					+	

- 1 Informed consent initially obtained for pre-operative MRI. Once eligibility confirmed, informed consent obtained for study registration
- 2 Physical Examination. Refer to Section 6.1.5
- 3 Enter details of all anti cancer therapy e.g. hormonal therapy, chemotherapy on the case record form
- 4 Renal function test (UEC) and eGFR. Performed within 28 days prior to pre-operative MRI scan and repeated prior to 18 month MRI scan
- 5 MRI must be performed within 6 weeks prior to first breast surgery and at 18 months post final breast surgery. Pre-menopausal women must not have a MRI scan between days 21 and 28 of their menstrual cycle. Refer to Appendix G for menopausal status
- 6 Mammogram must have been performed within 3 months prior to first excisional surgery and breast density on mammogram should be reported.
- 7 Report Adverse Events related to MRI/contrast only
- 8 Patients will continue to be followed every 6 months from 12-60 months post final excisional surgery and annually for up to 10 years or until the final analysis, whichever occurs first

6.3 Prior and Concomitant Therapy

Systemic hormone replacement therapy (HRT) must be ceased within 4 weeks of histological diagnosis of breast cancer. Topical HRT for severe symptoms is at the discretion of the clinician but must be clearly documented.

Patients will be eligible for enrolment in other clinical trials, with prior approval from the Study Chair.

6.4 Study Discontinuation

Patients will remain on the study unless consent is withdrawn.

7 SAFETY AND ADVERSE EVENTS

7.1 Adverse Events (AE)

An adverse event (AE) is any untoward medical occurrence in a trial patient. An AE does not necessarily have a causal relationship with the treatment or trial patient. An AE can therefore be any unfavourable and unintended sign (including an abnormal laboratory finding), symptom, or disease temporally associated with participation in a trial, whether or not related to that participation. This includes all deaths that occur while a patient is on a trial.

7.1.1 Adverse Event reporting for ANZ1002

Adverse Events related to the MRI procedure including MRI contrast only are to be reported. All other treatments/imaging are standard of care and therefore events are not to be reported to BCT.

Events due to breast cancer or its progression are study endpoints and are not categorised or reported as adverse events in this study.

As far as possible, each grade 1- 5 adverse event must be described by:

1. NCI-CTCAE (Version 4.0) terms – Common Terminology Criteria for Adverse Events (Refer to Appendix C).
2. Duration (start and end dates). The entire duration of the AE should be reported.
3. Severity Grade. The severity of each grade should be reported.
4. Whether the event was reported as a Serious Adverse Event (SAE).

Only adverse events that are NOT included in the NCI CTCAE v4.0 should be reported and graded under the “Other” adverse event within the appropriate category and graded as mild (Grade 1), moderate (Grade 2), severe (Grade 3), life threatening or disabling (Grade 4), or fatal (Grade 5) using the general definitions provided:

Table 2 Non-CTCAE severity grading

Grade	Severity	Description
1	Mild	Barely noticeable, does not influence functioning Causing no limitations of usual activities
2	Moderate	Makes participant uncomfortable, influences functioning Causing some limitations of usual activities
3	Severe	Severe discomfort, treatment needed Severe and undesirable, causing inability to carry out usual activities

4	Life threatening or disabling	Immediate risk of death
5	Fatal	Causes death of the participant

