7.2 Serious Adverse Event (SAE)

Serious Adverse Events related to the MRI procedure including MRI contrast only are to be reported. All other treatments/imaging are standard of care and therefore events are not to be reported to BCT.

[figure not shown]
A SAE is any adverse event (experience) or reaction or any untoward medical occurrence that fulfils one of the following:

- Is fatal (results in death)
- Life threatening (Note: the term “life-threatening” in the definition of “serious” refers to an event in which the patient was at risk of death at the time of the event. It does not refer to an event which could hypothetically have caused death had it been more severe)
- Required patient hospitalisation or prolongation of existing hospitalisation (Note: “inpatient hospitalisation” refers to an unplanned, overnight hospitalisation)
- Results in persistent or significant disability/incapacity
- Is a congenital anomaly/birth defect
- Is medically significant or requires intervention to prevent one or other of the outcomes listed above

Events not considered to be serious adverse events are hospitalisations occurring under the following circumstances:

- a) Planned before entry into the clinical trial for a pre-existing condition that is unrelated to the studied indication
- b) For elective treatment of a condition unrelated to the studied indication or its treatment
- c) Emergency and/or outpatient hospitalisation not resulting in admission (unless fulfilling the criteria of serious given above)
- d) Part of the normal treatment or monitoring of the studied indication and not associated with any deterioration in condition
- e) Admission to a hospital or other institution for general care, not associated with any deterioration in condition

Figure 4 SAE reporting flowchart

Abbreviations:

DQF = Data query form prepared by BCT in order to clarify or collect more information regarding the SAE report

F/U form = Follow up to original SAE report

SAE form = Serious adverse event (SAE) report prepared by investigator

Medical and scientific judgement should be exercised in deciding whether expedited reporting is appropriate in other situations, such as important medical events that may not be immediately life threatening or result in death or hospitalisation, but may jeopardise the patient or require intervention to prevent one of the outcomes listed in the definition above. These situations should usually be considered serious.

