In addition, in the ANZ 1002 PROSPECT protocol, there is additional monitoring for those who forgo radiotherapy (extra MRI at 18 months postoperatively and potentially MRI-directed biopsies). The extra MRI monitoring if this protocol was rolled out in practice may be lower than the current trial, particularly if rates of recurrence are low (i.e. additional MRI was included in the trial as an additional safety measure rather than as part of planned routine care if ANZ 1002 PROSPECT was implemented in practice). We will include a sensitivity analysis in the model to explore the possibility of additional ongoing monitoring costs of differing levels.

Sourcing costs

Procedure unit costs such as MRI and biopsies will be based on MBS costs or Royal Melbourne Hospital/The Royal Women's Hospital information on costs. Hospital inpatient stay unit costs will be estimated using Australian Refined Diagnosis Related Groups (AR-DRG) and Tier2 codes reported in the Australian Government Department of Health National Public Cost Weight Tables combined with the total average length of stay recorded for each procedure reported in the Royal Melbourne Hospital/The Royal Women's Hospital data. These average costs will then be directly applied to the observed hospital procedures (including adverse events etc.) used in the ANZ 1002 PROSPECT cohort and the matched control group.

Where required, and in particular where the MRI finds additional lesions, direct costs incurred after treatment for out-of-hospital services and prescription medicines that are not recorded in the available data will be estimated by using information from the Lifepool cohort (www.lifepool.org). A paper currently under review by [name], [name], Mann *et al.* has estimated the costs associated with treating early stage breast cancer using this cohort. Costs are estimated from date of diagnosis up to 5 years after diagnosis and include estimated costs by presented cancer characteristics at diagnosis (e.g. lymph node involvement, tumour size and presence of multiple tumours).

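### Adverse event reporting is limited to MRI and contrast on a standard-of-care ground that the protocol itself contradicts for BI-RADS 3 biopsies and for work-up after the 18-month MRI

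*Protocol*

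**What the plan says.** Section 7.1.1 sets the scope of reporting: "Adverse Events related to the MRI procedure including MRI contrast only are to be reported". The next sentence gives the reason: "All other treatments/imaging are standard of care and therefore events are not to be reported to BCT". Section 7.2 applies the same limit to serious events ("Serious Adverse Events related to the MRI procedure including MRI contrast only are to be reported") and repeats the reason. Footnote 7 of the Study Calendar in Section 6.2 shortens the rule to "Report Adverse Events related to MRI/contrast only".

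Other sections order tissue sampling on the strength of a study MRI:

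- **Section 6.1.1.1, pre-operative MRI.** On ordinary practice: "BI-RADS 3 lesions would ordinarily have a recommendation for 6 month follow up MRI scan". On this trial: "These lesions will be grouped with the BI-RADS 4 lesions and a tissue diagnosis is required".
- **Section 6.1.3.1.** An additional mass seen on MRI that has not had a core biopsy must undergo excisional biopsy at the primary operation.
- **Section 6.1.7, 18-month MRI.** For any additional enhancement or foci, "these will be investigated with targeted ultrasound and ultrasound or MRI-guided core biopsy to diagnose or exclude local recurrence".
- **Appendix I, part 4.** The monitoring added for women who forgo radiotherapy is described as "extra MRI at 18 months postoperatively and potentially MRI-directed biopsies". The appendix explains that this scan is a safety measure of the trial and not something foreseen for routine use.
- **Appendix I, Table 5.** Standard care carries no additional implementation cost. The MRI-screened group carries the cost of MRI and the cost of biopsy, including open biopsy.

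**The concern.** The reporting limit rests on a single reason: nothing beyond the MRI itself departs from standard care. If the same protocol describes some of the resulting biopsies as departures from, or additions to, that care, the reason fails for those procedures and the limit has no stated basis.

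A haematoma, an infection or an unplanned overnight admission after a biopsy done only because of a trial MRI would then not be reported. An admission of that kind would satisfy a seriousness criterion listed in Section 7.2 and still lie outside the reporting scope.

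This bears on the trial's wider purpose. Appendix J sets out to assess the overall impact of giving MRI to all and radiotherapy to some. Complications of work-up prompted by MRI are part of that impact, and the safety record as defined does not hold them.

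**Working it through.** No sample size, power or event figure is in dispute, so the check compares texts. A short calculation of scale follows.

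**1. Does the stated reason hold for each type of procedure?**

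- *Pre-operative BI-RADS 3 lesions.* No. Section 6.1.1.1 states ordinary practice and then departs from it.
- *Work-up after the 18-month MRI.* No. Appendix I classes both the scan and its potential biopsies as additional to what routine care would include.
- *MRI-triggered biopsy in general.* Table 5 treats it as an added cost against nil for standard care, and the introduction to Appendix I also calls these biopsies extra. The costing section and the safety section classify the same procedures differently.
- *Pre-operative BI-RADS 4 and 5 lesions, and the excision in Section 6.1.3.1.* Apart from Table 5's costing, no text says that work-up of such a lesion, once found, departs from usual care. There is no express contradiction here.

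**2. Could the reporting scope already include these biopsies?** Section 7.1.1 does not define what counts as related to the MRI procedure, and an MRI-guided biopsy might be argued in. Footnote 7 points to the narrower reading. Neither reading reaches an ultrasound-guided core biopsy or a surgical excision.

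**3. Are the complications collected elsewhere?**

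- Appendix H collects MRI, surgery and pathology data for all pre-registered patients and examines the impact on surgical management.
- Section 11.5 requires every death to be reported with date and cause.
- Appendix I applies costs to hospital procedures and mentions adverse events among them, for a cohort of about 400 women.
- Appendix J lists treatment, endocrine therapy and recurrence.

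These sources capture some consequences. None specifies a graded complication attributed to an MRI-driven biopsy or excision and reported to the sponsor.

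**4. Scale, for illustration only.** Inputs: 443 screened (Appendix K); additional foci on MRI in 16% (range 6–34%), of which 66% were malignant (meta-analysis cited in Section 1.1.4).

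- Women with additional foci: 443 × 0.16 = 70.9, about 71. Range: 443 × 0.06 = 26.6 to 443 × 0.34 = 150.6, about 27 to 151.
- Of these, not malignant: 70.9 × (1 − 0.66) = 24.1, about 24. Range: 26.6 × 0.34 = 9.0 to 150.6 × 0.34 = 51.2, about 9 to 51.

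These figures do not measure the contradicted subset. They count all additional foci, not BI-RADS 3 lesions. They borrow rates from other cohorts. The denominator includes women with more than mild background enhancement, to whom the tissue pathway in Section 6.1.1.1 does not apply. Work-up after 18-month MRIs, in up to 201 women, is not counted.

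**5. Timing.** 201 in the main study plus 242 ineligible (Appendix J) gives 443, the number screened. Appendix K reports follow-up of 24 to 120 months at the primary analysis. The minimum of 24 months exceeds 18, so essentially all study MRIs lie in the past.

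**The case against.** The strongest reply is that restricted event collection is a legitimate choice in a low-risk, single-arm trial without a study drug and with a recurrence endpoint, and that rewording Section 7 now would catch almost nothing. The second part stands: a prospective change alone recovers little, so the remedy must include retrieval from records or an explicit limitation. The first part would carry weight if the protocol gave it as the reason. The reason it does give is standard of care, and its own text contradicts that.

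Three stronger readings are tempting and are not supported:

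- *That these harms are captured nowhere, or are absent from the economic model.* A reader might infer this from Section 7. However, surgery data and deaths with cause are collected. Appendix I takes hospital procedures and adverse events into its costing without saying that they come from the sponsor's event forms. Table 5 also includes biopsy, additional excision and the quality-of-life effect of MRI with biopsy.
- *That the protocol places all MRI-driven biopsies and excisions outside usual care.* It says so expressly only for BI-RADS 3 lesions, and by description for the 18-month work-up. For additional lesions in general, Appendix I speaks of investigation and treatment as the treating team judged appropriate. Some pre-operative lesions may also have been removed in an operation already planned, so the added harm is uncertain.
- *That the data monitoring committee is deprived of safety data by this rule.* Section 10.2 gives its remit as interim analyses, accrual and local recurrence. Event listings are not mentioned, so wider reporting would not by itself change what it sees.

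**Conclusion.** The point holds in a limited form and should be acted on. The standard-of-care reason in Sections 7.1.1 and 7.2 is contradicted for the compulsory tissue diagnosis of BI-RADS 3 lesions and for the work-up of 18-month MRI findings, and it sits badly with Table 5 for MRI-triggered biopsy generally. Followed as written, the rule leaves complications of these trial-driven procedures out of graded, attributed safety reporting to the sponsor.

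The size of the gap cannot be computed. About 71 women with additional foci (27 to 151) and about 24 with benign findings (9 to 51) indicate an order of magnitude only, and only if the cited rates apply to this lower-risk population. It cannot be said that the MRI strategy will appear safer or cheaper than it is, only that the safety record could not show otherwise for these complications.

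The conclusion assumes that footnote 7 gives the intended reading of the scope. On a wider reading, MRI-guided biopsies would be covered, but ultrasound-guided biopsies and excisions still would not. No view is taken on which work-up is clinically right.

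**What to change.** 1. Correct the standard-of-care sentence in Sections 7.1.1 and 7.2, and reconcile it with Sections 6.1.1.1, 6.1.3 and 6.1.7, footnote 7 and Appendix I, so that the same procedures are classified alike for safety and for costing.
2. In the same three places (7.1.1, 7.2, footnote 7), make adverse and serious adverse events reportable when related to a biopsy or additional excision prompted by a finding on a study MRI, whether pre-operative or at 18 months.
3. For procedures already done, retrieve such events from existing records at the next planned data submission. Appendix J provides one for ineligible patients at each later analysis, the next being set for May 2026. Main-study patients need an equivalent request.
4. If retrieval is not undertaken, state the gap as a limitation on any safety or cost claim for the MRI strategy.

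The cost is a wording amendment, an attribution option on the event form, and modest extra site reporting or record review for a minority of patients. No procedure is added and patient management is unchanged.
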